#### **4.8 Study Discontinuation**

The Principal Investigator has the right to terminate this study at any time. Reasons for terminating the study may include the following:

- The incidence or severity of adverse events in this or other studies indicates a potential health hazard to subjects
- Subject enrollment is unsatisfactory

## 4.9 Statistical Methods

Number of referrals to PI, number of eligible participants, and number of enrollees will be used to monitor accrual. AEs and SAEs will be documented for all enrollees. All enrollees will be included in an intent-to-treat analysis. Pre-post tumor comparisons will be made among enrollees with both samples.

The study will use an exact binomial one-sided test to provide statistical measures to the outcomes.

### Analysis

Treatment outcome (Visual Function Score; Table 15) will be measured overall (primary endpoint). The **primary** outcome will be the assessment of the visual system using a weighted assessment scale per Table 15. A weighted score of 21 or more (out of possible 50) constitutes a successful outcome.

Exact binomial one-sided tests will be used to compare success rate of the primary outcome (Visual Function Score, Table 15) to 30% (a literature- and practice-based estimate of the loss of visual and lacrimal function after treatment of locally advanced periocular/orbital BCCA). If the true success rate is 50%, the study will have 90% power to reject the null hypothesis ( $p=0.3$ ) in favor of the alternative ( $p>0.3$ ) at  $\alpha=0.05$ .

Secondary endpoints will utilize the three treatment modality groups:

- #1: treatment stopped due to non-response (per RECIST);
- #2: treatment continued for a full year with good response and good tolerance
- #3: treatment stopped due to poor tolerance in spite of good response;

**Secondary** outcomes will utilize the actual numerical values obtained during the assessment over time to correlate visual function with tumor size (measured at each visit and/or via MRI/CT imaging). The secondary outcome measures will assess each part of the composite visual assessment score to determine changes in vision and lacrimal function following vismodegib treatment.

Histologic characteristics and molecular markers to be studied for the secondary objective include HMW keratin, proliferation markers such as Ki67, hedgehog and Wnt pathway markers. These will be summarized overall, by treatment modalities, and by outcome groups (e.g., Good or Poor Visual or Lacrimal Function). No other subgroup analyses are planned. **Please see page 20, BASIC RESEARCH ARM.**

### Safety Analysis

AEs and SAEs will be tabulated among all enrollees.

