## Phase II BCNS Study (SHH4685s)

The anti-BCC efficacy of vismodegib was tested in a randomized, double-blinded, placebo-controlled, Investigator-sponsored trial in Gorlin syndrome (BCNS) patients with surgically eligible BCCs (Tang et al. 2012). Forty-one patients were randomized 2:1 to receive oral vismodegib (n=26) or placebo (n=15). After a mean follow up of 8 months (range, 1 to 15 months), the per-patient rate of new surgically eligible BCCs (SEBs) was lower with vismodegib than with placebo (2 vs. 29 cases per group per year,  $p<0.001$ ), as was the size (percent change from baseline in the sum of the longest diameter) of existing clinically significant BCCs ( $-65\%$  vs.  $-11\%$ ,  $p=0.003$ ). In some patients, all BCCs clinically regressed. No tumors progressed during treatment with vismodegib. Patients receiving vismodegib routinely had Grade 1 or 2 AEs of loss of taste, muscle cramps, hair loss, and weight loss. Overall, 54% of patients (14 of 26) receiving vismodegib discontinued drug treatment due to AEs. At 1 month, vismodegib use had reduced the Hh pathway's target-gene expression in BCC cells by 90% ( $p<0.001$ ) and diminished tumor-cell proliferation, but apoptosis was not affected. No residual BCC was detectable in 83% of biopsy samples taken from sites of clinically regressed BCCs. At the second pre-specified interim analysis, a data safety and monitoring board concluded that the pre-determined threshold for a significant difference between the two groups had been reached ( $p<0.0113$ ), and the treatment with placebo in this arm was terminated. See the Vismodegib Investigator Brochure and the US package insert for additional details on nonclinical and clinical studies on vismodegib.

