Of the 500 patients, 107 (21.4%) experienced SAEs. The most common events were in the following system organ classes: infections and infestations, 30 patients (6.0%); neoplasms (benign, malignant, and unspecified, including cysts and polyps), 16 patients (3.2%); general disorders and administration site conditions, 12 patients (2.4%); nervous system disorders, 12 patients (2.4%); cardiac disorders, 11 patients (2.2%); injury, poisoning and procedural complications, 10 patients (2.0%); and metabolism and nutrition disorders, 10 patients (2.0%).

As of 6 November 2013, there have been 29 deaths among 500 safety-evaluable patients. The causes of death were PD in 4 patients, AE in 20 patients, and 5 patients with “other” as cause of death. Most patient deaths were considered unrelated to treatment with vismodegib. Two

deaths (cardiopulmonary arrest and cardiac infarction) were assessed by the investigator as related to vismodegib; however, both patients had significant risk factors and comorbidities. Both events were considered by the investigator to be related because of the temporal relationship between the onset of the event and administration of vismodegib; therefore, an association could not be excluded.

As of 6 November 2013, 400 of 500 patients (80%) treated during Study MO25616 had discontinued study drug. Reasons for discontinuation of study drug included: AE (178 patients, 35.6%); progression of disease (70 patients, 14.0%); patient request (62 patients, 12.4%); death (10 patients, 2.8%); investigator request (14 patients, 2.8%); lost to follow-up (4 patients, 0.8%); and other (62 patients, 12.4%).

The majority of patients (98.2%) in Study MO25616 (STEVIE) experienced TEAEs. The most common (>20%) TEAEs included muscle spasm (63.2%), alopecia (61.0%), dysgeusia (53.8%), weight decreased (32.4%), asthenia (28.2%), decreased appetite (25.4%), and ageusia (22.4%). Twenty-four (4.8%) Grade 4 events and 21 (4.2%) Grade 5 events were reported. Two of the deaths were considered related to vismodegib treatment (cardio-respiratory arrest and myocardial infarction). There were 107 (21.4%) patients who reported SAEs. Common SAEs that were reported in  $\geq 1\%$  of patients were pneumonia (1.8%, n=9), general physical health deterioration (1.4%, n=7), and dehydration (1.0%, n=5).

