## 4.3 Study Treatment

The study treatment will follow SOC protocol for BCCA that threatens the eye or lacrimal apparatus. The study aims to enroll 50 patients over 3 years and follow each patient for 1 year.

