### Vismodegib Dosage

Vismodegib is 150 mg taken QD PO until disease progression or until unacceptable toxicity. Vismodegib may be taken with or without food.

- **Swallow capsules whole**
- **Do not open or crush capsules**
- **If a dose of vismodegib is missed, do not make up that dose; resume dosing with the next scheduled dose.**

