### **Assessment of Adverse Events**

All AEs and SAEs whether volunteered by the subject, discovered by study personnel during questioning, or detected through physical examination, laboratory test, or other means will be reported appropriately. Each reported AE or SAE will be described by its duration (i.e., start and end dates), regulatory seriousness criteria if applicable, suspected relationship to the study drug (see following guidance), and actions taken.

To ensure consistency of AE and SAE causality assessments, investigators should apply the following general guideline:

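### The safety analysis is a single all-enrollee tabulation with no account of time on drug, so its percentages would understate late-onset harms if read as the risk over a full year of vismodegib

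*Combined protocol and SAP*

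**What the plan says.** Section 4.9 opens its safety provision with "AEs and SAEs will be documented for all enrollees", and its Safety Analysis paragraph consists only of "AEs and SAEs will be tabulated among all enrollees". Section 4.9 names no person-time, onset-time, cumulative-incidence or treatment-duration summary. After the marker summaries, the Analysis paragraph adds "No other subgroup analyses are planned".

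On exposure, section 4.3 states "The study aims to enroll 50 patients over 3 years and follow each patient for 1 year" and, under Vismodegib Dosage, "Vismodegib is 150 mg taken QD PO until disease progression or until unacceptable toxicity". Section 4.9 then sets out three treatment groups. Only group #2 takes the drug for the full year; #1 stops for non-response and #3 for poor tolerance.

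On observation of AEs, the Adverse Event Reporting Period in section 5.2 closes 30 days after the last dose or at study discontinuation, whichever comes first. Section 4.7 has patients who stop, do not restart within 30 days and refuse surgery leave the study at an evaluation within a month of stopping.

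On what is recorded, section 5.2 says: "Each reported AE or SAE will be described by its duration (i.e., start and end dates". Table 16 schedules an AE assessment every month.

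**The concern.** A patient who stops at month 3 is under AE observation for about 91 + 30 = 121 days, yet would count in an all-enrollee denominator just like a patient observed for a year. Table 8 (expanded access study) gives median onset among affected patients of 37 days for muscle spasms, 87 for alopecia and 175 (95% CI 114 to 293) for weight decrease. Early stoppers therefore have most of their chance to show a spasm but less than half of their chance to show weight loss.

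The background reports substantial stopping. In the large phase II safety study, "400 of 500 patients (80%) treated during Study MO25616 had discontinued study drug", with 35.6% of patients stopping for AEs. In the Gorlin syndrome trial, "54% of patients (14 of 26) receiving vismodegib discontinued drug treatment due to AEs". In the pivotal study's locally advanced cohort, 22.5% stopped for AEs (Table 5).

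At stake is how the harms table will be read. The study follows patients for a year of intended treatment, and a reader will naturally take the percentages as the harm to expect from that year. For late harms they would be too low, by an amount that depends on how early patients stopped, and the table would not show that.

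**Working it through.** **The plan's own figure.** The safety section states none. The only calculation in the plan is the efficacy power: exact one-sided binomial, n = 50, 0.3 against 0.5, alpha 0.05. The smallest rejecting count is 21, with exact alpha 0.0478 and power 0.8987. This agrees with the stated 90% and plays no part in what follows.

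**Inputs from the documents.** Median onset of 175 days (weight decrease) and 37 days (muscle spasms), Table 8. AE window of 30 days after last dose, section 5.2. Illustrative weight-decrease risks of 51.0% (Table 6) and 32.4% (the large phase II safety study).

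**Assumptions.**
- Those percentages, and 70% for spasms, stand in for the 12-month on-drug risk P. They are really crude figures at data cutoffs.
- The fraction d who stop within 12 months is not given in the plan, so a range is used.
- Stopping is exponential and independent of onset.

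**Formula.** With onset distribution F and stopping rate λ = −ln(1 − d)/365, the expected all-enrollee proportion is

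crude = ∫₀³⁶⁵ exp(−λ·max(t − 30, 0)) dF(t).

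F is Weibull, F(t) = 1 − exp(−(t/b)^k), fixed by F(365) = P and F(median) = P/2. This gives:
- weight decrease, P = 51%: k = 1.204, b = 483 days
- weight decrease, P = 32.4%: k = 1.082, b = 868 days
- muscle spasms, P = 70%: k = 0.449, b = 241 days

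**Results** (crude percentage, relative shortfall in brackets).

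| Stopped by month 12 | Weight, P = 51% | Weight, P = 32.4% | Spasms, P = 70% |
|---|---|---|---|
| 22.5% | 46.1% (10%) | 29.3% (10%) | 67.3% (4%) |
| 35% | 43.0% (16%) | 27.4% (16%) | 65.6% (6%) |
| 50% | 39.1% (23%) | 24.9% (23%) | 63.3% (10%) |
| 65% | 34.5% (32%) | 22.0% (32%) | 60.6% (13%) |

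In patients, with 50 enrolled and P = 32.4%, the expected count is 16.2 for a full year on drug. The table would show 14.6 if 22.5% stop and 11.0 if 65% stop.

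**Sensitivity to the onset model.** A truncated-exponential onset with the same medians gives weight shortfalls of 10% at d = 22.5% and 32% at d = 65%, and spasm shortfalls of 2% and 8%. The direction and ranking are unchanged; the spasm figure depends more on the onset shape.

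**Sensitivity to independence.** Suppose half of those who stop do so because of their own weight loss. Those events are counted, so only the other half remove observation time. At P = 32.4% the crude figure is then roughly 30% rather than 27% with 35% stopped, and roughly 28% rather than 25% with 50% stopped. The shortfall falls by about a third to a half.

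**The case against.** The strongest reply is that nothing is biased. No primary or secondary objective concerns safety, the drug is given as standard of care, and no decision rule rests on the AE table. A proportion of all enrollees correctly describes what happened to patients as treated. That stands: the percentage is too low only as an estimate of full-year on-drug risk, which the plan never claims to estimate. It is also true that the text says only that events are tabulated, so a percentage of all enrollees is an inference, though the natural one.

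The size may be modest. With 22.5% stopping, 32.4% becomes 29.3%, about 1.6 patients in 50, against a 95% half-width of 1.96·√(0.324 × 0.676/50) = 13 points. The higher stopping figures transfer poorly: the 80% is cumulative to a data cutoff, and the 54% comes from Gorlin syndrome patients. The 22.5%, for its part, counts AE-related stops only. This also stands, and is why the result is given as a range.

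A reader might infer two stronger points that the documents do not support.
- **Late onset explains the spread in background weight loss** (15.8%, 32.4% and 51.0% across three studies, while spasms stay near 63 to 71%). Early-onset events vary too: fatigue (median 42 days) is 42.3% in Table 6 against 19.2% in Table 8, and nausea (30 days) is 32.7% against 19.2%. The background rates are also plain percentages of patients, so the crude table remains the like-for-like comparison.
- **The point holds under any AE reporting window.** If AEs were collected for the full year whatever the drug status, observation time would be equal and the proportion would be a proper one-year as-treated risk. Section 4.5 does speak of follow-up regardless of treatment status, but sections 4.7 and 5.2 close observation soon after stopping. The point rests on the section 5.2 window.

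Finally, the dates are already collected, so time-based summaries could be added at reporting. That is so, but naming them in advance settles the method before the data are seen.

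**Conclusion.** The point holds as a cheap improvement to safety reporting, not as an error in the plan. The single planned tabulation is valid as as-treated risk. Read as the risk over a planned year on drug, it understates late harms more than early ones: for weight decrease by about 10% (relative) if 22.5% stop within the year and about 32% if 65% stop, against about 4% and 13% for muscle spasms. These figures assume independent exponential stopping, the 30-day window, Table 8 onset medians, and cited crude rates used as one-year risks. The true size cannot be fixed, because the plan gives no stopping rate, and it is smaller where the AE itself causes the stop. It would be going too far to conclude that the planned percentages are wrong in themselves. The primary efficacy test is untouched.

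**What to change.** In section 4.9, Safety Analysis, keep the all-enrollee table and label it as risk as treated. Add beside it:

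- (a) the distribution of time on drug (for example median, quartiles, and number still on drug at months 3, 6, 9 and 12);
- (b) for SAEs and for each AE term seen in at least 10% of patients, the number of patients with a first event per 100 patient-months at risk;
- (c) for the same events, cumulative incidence of first event at months 3, 6, 9 and 12 from first dose, with numbers at risk, censored at end of exposure plus the reporting window, and a stated caveat that stopping may be informative.

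A version treating the end of exposure plus window as a competing event need not be added for month 12. Absent other loss to follow-up, it equals the crude proportion there.

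Cost: a few sentences of SAP wording and one extra table. AE dates are already required by section 5.2; first and last dose dates are the only other input. No new data, visits or staff are needed. The downsides are wide intervals with 50 patients, especially at month 12, and a censored estimate that must be read with its caveat.

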### **Missing Data**

Pre-treatment data will be reviewed prior to enrollment to ensure that all the required elements are documented. Incomplete post-treatment data will be completed via subsequent clinical exam and/or telephone interview.

### **Determination of Sample Size**

- *Endpoints used*

The endpoint used for determining sample size was a Visual Assessment Weighted Score of at least 21 (out of possible 50).

- *Methodology used*

The exact binomial one-sided test with  $n=50$  has 90% power to reject the null hypothesis  $p=0.3$  in favor of the alternative  $p=0.5$  at  $\alpha=0.05$ .

A recruitment assessment will be performed at the 2 and 3 year time points (out of 4 years), in order to assess recruitment. The goal of the study is to enroll 50 patients over 3 years, or 16-17 patients per year. After year 1, if recruitment drops below a minimum 12 patients (or at least one per month on average) then the study will be adjusted by (1) extending the trial beyond 3 years of recruitment, and/or (2) extending patient recruitment to outside medical institutions. After year 2, if recruitment is greater than 20 but below 30 patients, then the trial will be extended by 1 year. If recruitment is below 20 patients at the end of year 2 then the trial will be both extended by 1 year and patient recruitment extended to outside institutions.

## **4.10 Data Quality Assurance**

Accurate, consistent, and reliable data will be ensured through the use of standard practices and procedures.

## **5. REPORTING OF ADVERSE EVENTS**

### **5.1 Assessment of Safety**

This study will be monitored in accordance with the NCI approved University of Michigan Rogel Cancer Center Data and Safety Monitoring Plan.

The study team will meet quarterly or more frequently depending on the activity of the protocol. The discussion will include matters related to the safety of study participants (SAE/UaP reporting), validity and integrity of the data, enrollment rate relative to expectations, characteristics of

participants, retention of participants, adherence to the protocol (potential or real protocol deviations) and data completeness. At these regular meetings, the protocol specific Data and Safety Monitoring Report form will be completed and signed by the Principal Investigator or by one of the co-investigators.

Data and Safety Monitoring Reports will be submitted to the University of Michigan Rogel Cancer Center Data and Safety Monitoring Committee (DSMC) on a quarterly basis for independent review.

### **Specification of Safety Variables**

Safety assessments will consist of monitoring and reporting AEs and SAEs per protocol. This includes all events of death, and any study specific issue of concern.

### **Adverse Events**

An AE is any unfavorable and unintended sign, symptom, or disease temporally associated with the use of an investigational medicinal product (IMP) or other protocol-imposed intervention, regardless of attribution.

This includes the following:

- AEs not previously observed in the subject that emerge during the protocol-specified AE reporting including signs or symptoms associated with basal cell carcinoma that were not present prior to the AE reporting period.
- Complications that occur as a result of protocol-mandated interventions (e.g., invasive procedures such as cardiac catheterizations).

If applicable, AEs that occur prior to assignment of study treatment associated with medication washout, no treatment run-in, or other protocol-mandated intervention.

Preexisting medical conditions (other than the condition being studied) judged by the investigator to have worsened in severity or frequency or changed in character during the protocol-specified AE reporting period.

### **Serious Adverse Events**

An AE should be classified as an SAE if the following criteria are met:

- It results in death (i.e., the AE actually causes or leads to death).
- It is life threatening (i.e., the AE, in the view of the investigator, places the subject at immediate risk of death. It does not include an AE that, had it occurred in a more severe form, might have caused death.).
- It requires or prolongs inpatient hospitalization.

- It results in persistent or significant disability/incapacity (i.e., the AE results in substantial disruption of the subject's ability to conduct normal life functions).
- It results in a congenital anomaly/birth defect in a neonate/infant born to a mother exposed to the IMP.
- It is considered a significant medical event by the investigator based on medical judgment (e.g., may jeopardize the subject or may require medical/surgical intervention to prevent one of the outcomes listed above).

## **5.2 Methods and Timing for Assessing AND Recording Safety Variables**

The investigator is responsible for ensuring that all AEs and SAEs that are observed or reported during the study are collected and reported to the appropriate IRB(s), in accordance with CFR 312.32 (IND Safety Reports).

### **Adverse Event Reporting Period**

The study period during which all AEs and SAEs must be reported begins after informed consent is obtained and initiation of vismodegib treatment and ends 30 days following the last administration of vismodegib or study discontinuation/termination, whichever is earlier. After this period, investigators should only report SAEs that are attributed to prior study treatment.

### **Assessment of Adverse Events**

All AEs and SAEs whether volunteered by the subject, discovered by study personnel during questioning, or detected through physical examination, laboratory test, or other means will be reported appropriately. Each reported AE or SAE will be described by its duration (i.e., start and end dates), regulatory seriousness criteria if applicable, suspected relationship to the study drug (see following guidance), and actions taken.

To ensure consistency of AE and SAE causality assessments, investigators should apply the following general guideline:

#### **Yes**

There is a plausible temporal relationship between the onset of the AE and administration of vismodegib, and the AE cannot be readily explained by the subject's clinical state, intercurrent illness, or concomitant therapies; and/or the AE follows a known pattern of response to vismodegib; and/or the AE abates or resolves upon discontinuation of vismodegib or dose reduction and, if applicable, reappears upon re-challenge

#### **No**

Evidence exists that the AE has an etiology other than vismodegib (e.g., preexisting medical condition, underlying disease, intercurrent illness, or concomitant medication); and/or the AE has no plausible temporal relationship to vismodegib administration (e.g., cancer diagnosed 2 days after first dose of vismodegib).

Expected adverse events are those adverse events that are listed or characterized in the Package Insert or current Investigator's Brochure.

Unexpected adverse events are those not listed in the Package Insert or current Investigator's Brochure ( or not identified. This includes adverse events for which the specificity or severity is not consistent with the description in the Package Insert or current Investigator's Brochure. For example, under this definition, hepatic necrosis would be unexpected if the Package Insert or Investigator's Brochure only referred to elevated hepatic enzymes or hepatitis.

